- Cohort 1: Subjects from group 1 and group 2 will be scheduled for three study sessions as described below. A screening visit, an MR spectroscopy scan without hyperinsulinemic clamp (euglycemia) and an MR spectroscopy scan during a hyperinsulinemic clamp (hypoglycemia) with a tracer infusion.
- Cohort 2: Subjects from group 1 and group 2 will be scheduled for two study sessions. A screening visit as described below. An MR spectroscopy scan that will be conducted during a hyperinsulinemic clamp (combined eu- and hypoglycemia) together with a tracer infusion.
- Cohort 3: Subjects from group 1 and group 2 will be scheduled for two studysessions. A screening visit as described below. An MR spectroscopy scan conducted during a hyperinsulinemic clamp (combined eu- and hypoglycemia) without a tracerinfusion.
- Cohort 4: Healthy subjects from group 2 will be scheduled for one study session. They will undergo an MR spectroscopy scan without a hyperinsulinemic clamp nor any other i.v. infusions (i.e. no i.v. infusions at all).
- Cohort 5: Subjects from group 1 and group 2 will be scheduled for two studysessions. A screening visit as described below and a hyperinsulinemic clamp together with a non-labeled ketone or saline infusion without an MR spectroscopy scan.

Session A: Screening visit (YNHH Clinical Research Unit):

At the screening visit, study subjects in both the control and T1DM groups will complete the informed consent form for participation in voluntary clinical research. Demographic and clinical data collected will be reviewed by study personnel to confirm eligibility.

Once consented, all subjects will be further screened with a medical history & physical examination, blood work (electrolytes, hematocrit, creatinine, liver function tests and HbA1c) and a 12-lead electrocardiogram (EKG). Detailed subject inclusion and exclusion criteria are listed below (Human subjects – Subject recruitment). Subjects in the T1DM group only will be instructed to record their glucose readings to determine degree and frequency of hypoglycemia as described above. The subject will perform the preliminary cognitive tests at this point if they are selected for Cohort 5 at this point. The two subsequent MR sessions to complete the study will be scheduled at this point. The subject in the control group will have their two MR sessions scheduled without having to record any glucose readings.

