Session B: NMR spectroscopy without tracer infusion (Magnetic Resonance Research Center)

Subjects may be scheduled to arrive on the evening before the study if arriving early will be a difficulty. If such a case occurs, subjects will be admitted to the HRU for an overnight stay to be there for the morning without any delay.

On the morning of study, subjects will arrive directly at the MRRC. A member of the research team will verify that if the subject is from the T1DM group, the diabetic subject (as previously instructed) has taken his/her normal morning dose of insulin (or has continued to wear the insulin pump). This will not apply to subjects that are from the control group of non-diabetics participants. A urine pregnancy test will be completed on all female subjects of child bearing potential. Any female testing positive will be excluded from the study. All subjects will meet the staff, study procedures will be reviewed, and they will be exposed to the instrumentation and then placed in the scanner for NMR spectroscopy.

Imaging Procedures with the 4T/ 7T Bruker Advance NMR spectrometer (Bruker Instruments, Inc, Bellerica, MA) with a 94 cm bore: Proton MRS will be performed using the outer 1H decoupling coils of the ¹³C probe at 4T. Parameters and pulse sequences for GABA and glutamate acquisition will be the standard ones presently being established for this coil by Drs [name] and [name]: Subjects will lie supine with the occipital cortex against a 7-cm surface coil tuned to ¹H-MRS frequency of 170.4 MHz. T₁-weighted images 30 seconds in duration will be acquired for subject positioning. 1st and 2nd order shimming will be performed automatically using the FASTERMAP procedure. We will then proceed to acquiring proton NMR spectra from a volume adjacent to the NMR coil for a period of 60 minutes. Total and regional power deposition will be below the FDA safety limits for RF power deposition. For 7T studies the pulse sequence will be performed using the multi Tx coil using pulse sequences and parameters established by Dr [name], which will be verified regarding local power deposition using RF simulations. The 7T studies will be exploratory.

Session C: NMR spectroscopy with ¹³C/ ²H -tracer infusion (Magnetic Resonance Research Center)

[figure not shown]

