Non-diabetic control subjects will be asked to remain fasting from midnight prior to the study. Upon arrival to the MRRC, their blood glucose will be checked and an IV catheter will be inserted for infusion of insulin and glucose to maintain normal glucose levels and the study will ensue as described below.

For type 1 diabetic subjects receiving insulin via an insulin pump, they will be asked to check their blood glucose at home before bed and on awakening to ensure that the glucose level is above 70mg/dl and below 200mg/dl. They will be instructed to call [name] with any readings outside of this range. Upon arrival to the MRRC, their blood glucose will be checked as a safeguard, and insulin received via the insulin pump will be held. An IV catheter will be inserted for infusion of insulin and glucose to maintain normal glucose levels and the study will ensue as described below.

For type 1 diabetic subjects using multiple injections of insulin per day will be asked to ensure that the glucose level is above 70mg/dl and below 200mg/dl. As a safeguard, they

will be asked to check their blood glucose at home before bed and on awakening. Upon arrival to MRRC, their blood glucose will be checked; a nurse will place intravenous (IV) line to start infusions of glucose and insulin to maintain normal glucose levels.

At 9:00 AM on the day of this NMR session, a standard IV catheter will be inserted and used to deliver a continuous

MRS study design. After a set up period of approximately 30 minutes that includes a 1H MRS scan, subjects will be infused for 120minutes with the isotopic labeled substrate.

insulin infusion (2mU/kg/min) and a variable infusion of 20% dextrose. In addition a second IV line will be placed in the opposite arm to receive a normal saline solution and provide access for obtaining blood samples.

Once subjects arrive in the MR center they will be brought to a hypoglycemic state. The plasma glucose level will be gently lowered to 50 ± 3 mg/dL (see blood draw schedule below).

Once hypoglycemia is achieved tracer will be administered (see Figure above). Depending on the cohort assignment this will involve one of the following infusions:

 a) A 200mmol/l ¹³C /²H- alternate substrate infusion, which will be delivered through a port in the already-established IV site at a rate of 22μM/kg/min.

or

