b) A 20% [1-¹³C]/ [²H]-glucose infusion at the same rate as the 20% unlabeled glucose infusion that is part of the ongoing hyperinsulinemic clamp. This 'clamp glucose' infusion will be held for the duration of the ¹³C/ ²H -glucose tracer infusion. In addition to the ¹³C/ ²H -glucose infusion subjects will receive a simultaneous infusion of unlabeled 350mM lactate (see adjacent Figure).

[figure not shown]

Figure 11: A) Study groups B) Timeline for hyperinsulinemic hypoglycemic clamp and tracer infusions.

Subjects will be moved into the scanner for magnetic resonance spectroscopy (MRS) studies. During the spectroscopy studies, subjects will lie supine in a 4.0 T 94 cm bore magnet. The back of each subject's head

will be superjacent to an 8 cm diameter ¹³C/²H-surface coil receiver with a half quadrature coil ¹H decoupling channel. Before the ¹³C/²H MRS measurements, an MRI will be obtained for localization purposes. From the image, a 48 cubic centimeter volume in the medical occipital-parietal lobe will be selected to obtain localized ¹³C/²H MRS spectra. The Bo homogeneity in the selected volume will be reduced to less than 0.08 ppm using automated shimming. Following shimming, localized MRS will be performed to the steady state ¹³C/²H-concentrations and fractional enrichments of ¹³C/²H-tracer, and the 2, 3, and 4 positions of aspartate, glutamate, and glutamine. Throughout the study, samples of plasma will be obtained for measurement of glucose, insulin, ketones, lactate, ¹³C enrichment metabolites, and counterregulatory hormones (glucagon, epinephrine, and norepinephrine, cortisol). (See sample collection table Appendix A.) In addition, autonomic and neuroglycopenic symptoms will be assessed.

When the study is completed, subjects will receive a bolus and infusion of 10% dextrose to restore normoglycemia; they will then return to the HRU, where they will eat lunch. Once each subject appears clinically well with stable blood glucose levels above 70 mg/dL for at least 60 minutes, the IV cannula can be removed and providing they are considered stable by the study physician, they can be discharged from the HRU.

Session D: Hyperinsulinemic Clamp with Cognitive Testing (Hospital Research Unit)

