Data analysis will be performed using SAS statistical software version 8.2. Prior to the fundamental analysis, all data will be appropriately screened for accuracy, missing data, outliers and agreement with assumptions for the analyses. Univariate descriptive statistics and plots will first be employed to determine out-of-range values as well as plausible means and standard deviations. Non-normal variables will be identified through the inspection of normal probability plots and with the Kolmogorov-Smirnov test. If required, appropriate transformations or non-parametric tests will be applied to variables in violation of the model assumptions. [name]., the GCRC biostatistician, is available for advice in data analysis.

To test the hypothesis that patients with hypoglycemia unawareness exhibit enhanced CNS ketone body metabolism we will assess brain beta-hydroxybutyrate transport and its absolute levels and the ratio of brain beta-hydroxybutyrate contribution to the neuronal and astroglial TCA cycle. In addition, we will determine the absolute concentration of brain neurotransmitter levels using proton NMR. Group comparisons will be assessed by analysis of variance (ANOVA) for repeated measures. Data will be tested for multisample sphericity using Mauchly's and Box tests. If the assumption of homogenous covariance matrices is violated a covariance pattern model will be employed to allow for separate sets of covariance parameters for type 1 diabetic vs. nondiabetic controls. Evaluation of a significant diagnosis by clamp condition interaction will be determined by paired or unpaired t-tests (for within and between subjects factors respectively), using the interaction variance term from the ANOVA with a Holm correction for multiple testing.

involvement.		
Children		Fetal material, placenta, or dead fetus
☐ Non-English Speaking	Prisoners	☐ Economically disadvantaged persons
Decisionally Impaired	Employees	Pregnant women and/or fetuses
☐ Yale Students		earing potential
		en who are wards of the state as potential subjects? Yes
No (If yes, see Instructions	section VII #4 for further	requirements)

7. Subject classification: Check off all classifications of subjects that will be targeted for enrollment in the

8. Inclusion/Exclusion Criteria: What are the criteria used to determine subject inclusion or exclusion?

Inclusion criteria for subjects:

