- 11.5 To avoid excess hypoglycemia during the hyperinsulinemic clamp, plasma glucose will be checked every five minutes using a bedside glucose monitor. Based on these measurements, the plasma glucose will be adjusted via the D20 infusion.
- 11.6 All potential study subjects will also be screened for MR safety using the standard MR safety protocol developed by Yale New Haven Hospital's Diagnostic Imaging department. Subjects with claustrophobia or with contraindications to MR scanning will be excluded from the study. The MR safety screening process will be performed both during the screening interview and on the day of an MR study.
- 11.7 To reduce MRI risks we require that all people involved with the study remove all metal from their clothing and all metal objects from their pockets. Nothing metal can be brought into the magnet room at any time. Subjects will also walk through a ferromagnetic detector. Also, once subjects are in the magnet, the door to the room will be closed so that no one from outside accidentally goes near the magnet. In addition, patients can stop study at any time if anxiety is a significant issue.
- 11.8 To reduce the risk of injury in the MRI scanner, subjects will go through a ferromagnetic metal detector, to prevent any metal objects being taken into the scanner.
- 11.9 Stable isotope infusions will be prepared in sterile form by the YNHH pharmacy and will be tested for pyrogenicity and sterility prior to use.

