B.1	Start insulin/ start clock	Glucose is checked every 5 minutes	X	X	X				Enter scanner
B.2	B.1 +30	X	X	X	X				
B.3	B.1 +60	X	X	X	X				
B.4	B.1 +90	X	X	X	X				
C.1 BHB Baseline	Start BHB infusion	Glucose is checked q5 min	X	X	X	X	X	X	Target glucose ~55mg/dl
C.2	C.1 +5	\downarrow				X			
C.3	C.1 +10	1				X			↓
C.4	C.1 +15	1				X			↓
C.5	C.1 +30	1	X	X	X	X	X		↓
C.6	C.1 +60	1	X	X	X	X	X	X	↓
C.7	C.1 +90	1	X	X	X	X	X		 
C.8	C.1 +120	Glucose check	X	X	X	X	X	X	End Clamp

COHORT 1:

Schedule of Events:	Screening Visit Session A	Proton-NMR Spectroscopy Session B	Carbon 13-NMR Spectroscopy Session C	Total Blood Collected
Informed Consent	X			
Medical History	X			
Physical Exam	X			
EKG	X			
Hematocrit (3 mLs)	X (3mLs)			
Creatinine (2 mLs)	X (2mLs)			
Liver Function Tests (3mLs)	X (3mLs)			
HbA1c (3mLs)	X (3mLs)			
Inclusion/Exclusion Check list	X			
Record Blood Sugar Levels 5x daily *	X			
Complete questionnaire for glucose readings <54mg/dl *	X			
Schedule two MR sessions	X			
Urine Pregnancy (females)	X	X		
IV Placement			X	
Hypoglycemic Clamp			X	
Blood Volume per visit	11 ml	none	< 250ml	< 250ml

^{*:} For diabetic subjects only

COHORT 2:

Schedule of Events:	Screening Visit	Carbon 13-NMR Spectroscopy	Total Blood Collected
Informed Consont	Session A	Session C	
Informed Consent	X		
Medical History	X		
Physical Exam	X		
EKG	X		
Hematocrit (3 mLs)	X (3mLs)		
Creatinine (2 mLs)	X (2mLs)		
Liver Function Tests (3mLs)	X (3mLs)		
HbA1c (3mLs)	X (3mLs)		
Inclusion/Exclusion Check list	X		
Record Blood Sugar Levels 5x daily *	X		
Complete questionnaire for glucose readings <54mg/dl *	X		
Schedule MR sessions	X		
Urine Pregnancy (females)	X	X	
IV Placement		X	
Hypoglycemic Clamp		X	
Blood Volume per visit	11 ml	< 250ml	< 250 ml

^{*:} For diabetic subjects only

COHORT 3:

Schedule of Events:	Screening	Proton-NMR	Total Blood
	Visit	Spectroscopy	Collected
	Session A	Session B	
Informed Consent	X		
Medical History	X		
Physical Exam	X		
EKG	X		
Hematocrit (3 mLs)	X (3mLs)		
Creatinine (2 mLs)	X (2mLs)		
Liver Function Tests (3mLs)	X (3mLs)		
HbA1c (3mLs)	X (3mLs)		
Inclusion/Exclusion Check list	X		
Record Blood Sugar Levels 5x daily *	X		
Complete questionnaire for glucose readings <54mg/dl *	X		
Schedule MR sessions	X		
Urine Pregnancy (females)	X	X	
IV Placement		X	
Hypoglycemic Clamp		X	
Blood Volume per visit	11 ml	< 250ml	< 250 ml

^{*:} For diabetic subjects only

COHORT 4:

Schedule of Events:	Screening Visit Session A	Proton-NMR Spectroscopy Session B

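### Cohort 1's unclamped Session B scan is labelled euglycemic, but for T1DM subjects on their usual insulin the plan writes no glucose reading and no low-glucose action

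*Combined protocol and SAP*

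**What the plan says.** Section V.4 (Research Plan) describes one of Cohort 1's two scans as "an MR spectroscopy scan without hyperinsulinemic clamp (euglycemia"). The other is done under clamped hypoglycemia with a tracer.

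The unclamped scan is Session B. Its text has a team member verify that a T1DM subject "has taken his/her normal morning dose of insulin (or has continued to wear the insulin pump"). A urine pregnancy test for women, orientation and 60 minutes of proton spectra follow. The Cohort 1 Schedule of Events marks only the pregnancy test for Session B. Its blood-volume row reads "Blood Volume per visit 11 ml none < 250ml < 250ml", where the columns are Sessions A, B and C and the total.

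Other parts of the plan do write glucose rules:

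- **Session C, pump users:** "Upon arrival to the MRRC, their blood glucose will be checked as a safeguard". Controls and injection users are also checked on arrival.
- **Session C, discharge:** "Once each subject appears clinically well with stable blood glucose levels above 70 mg/dL for at least 60 minutes" is a condition for removing the cannula and going home.
- **Sessions C and D:** a 70-200 mg/dL home range for T1DM subjects, and an overnight fast for controls.
- **Section V.11.5:** "To avoid excess hypoglycemia during the hyperinsulinemic clamp, plasma glucose will be checked every five minutes using a bedside glucose monitor".

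The Statistical Considerations (Section V.6) add that "we will determine the absolute concentration of brain neurotransmitter levels using proton NMR".

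**The concern.** **Safety.** Group 1 is chosen for severe past hypoglycemia and for unawareness of it. In Session B these subjects have taken their full usual insulin, have no written meal instruction, and lie in a magnet for at least an hour. The cover in place responds to signs: a nurse at the subject's side, a practitioner in view, a crash cart, and pulse, oxygen and blood-pressure monitoring. Early signs are what these subjects tend to lack, and none of these measures shows a falling glucose.

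**Interpretability.** The scan is called euglycemic, but nothing written establishes or records that state in the T1DM group. If their glucose differed from that of controls, a group difference in a metabolite that follows glucose could not be told apart from an effect of diagnosis. A reading that was never taken cannot be recovered at analysis.

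**Working it through.** The core check is textual.

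**1. Written glucose rules, by session**

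| Item | Session B, Cohort 1 | Session C | Session D |
|---|---|---|---|
| Arrival glucose check | none written | yes | yes |
| Acceptable range, T1DM | none written | 70-200 mg/dL at home | 70-200 mg/dL at home |
| Meal or fasting rule | none written | controls fast | controls fast |
| T1DM insulin | usual dose or pump kept on | pump held on arrival | basal cut by about 15%, or evening dose halved and morning dose skipped |
| Checks during the session | none written | every 5 minutes (clamp) | every 5 minutes (clamp) |

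The four-week home log in Section V.4 feeds the HYPO score at enrollment. It is not a Session B reading.

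**2. Scope.** Cohort 3's schedule also heads its scan column Session B, but marks an IV line and a clamp. Cohort 2 reaches both glycemic states inside the clamp. Cohort 4 enrols healthy subjects only. Cohort 5 has no scan. So Cohort 1 is the only cohort in which T1DM subjects are scanned without a clamp. Session B carries no tracer, so the ketone endpoint does not draw on it.

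**3. Why no bias figure can be given.** Suppose a metabolite changes by β per mg/dL in both groups, and let G_T and G_C be the mean Session B glucose in T1DM subjects and controls. With the clamp at 50 mg/dL in both groups, the spurious group difference in eu- to hypoglycemic change is

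β × [(G_T − 50) − (G_C − 50)] = β × (G_T − G_C).

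The documents give neither β nor the two means. As an assumption, borrow the home range for Session B. An individual T1DM step to 50 mg/dL could then lie anywhere from 70 − 50 = 20 to 200 − 50 = 150 mg/dL. If β is zero over that range, or the group means agree, the bias is zero.

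**4. Why a 70-200 entry rule is not a bias control.** It admits every value in the span just used, so G_T − G_C is not constrained beyond what was assumed. It is a safety and plausibility limit.

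**5. What glucose adjustment would cost.** The plan's own power figure comes first: 17 per group, difference 0.033, SD 0.033, two-sided 0.05 gives t-test power 0.807, against the stated 80%. With Session B glucose as a covariate and a common slope, the standard error of the group contrast is multiplied by √[1 + (n/2)·D²/W]. Here D is the difference in group mean glucose and W the within-group sum of squares. Assumed spreads, not in the documents: T1DM uniform over 70-200 (mean 135, variance 130²/12 = 1408.3), n = 17.

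- Controls 80-100: D = 45, W = 16 × (1408.3 + 33.3) = 23,067, factor √(1 + 8.5 × 2025/23,067) = 1.32.
- Controls 80-140: D = 25, W = 16 × (1408.3 + 300) = 27,333, factor 1.09.
- Controls 90-140: D = 20, W = 16 × (1408.3 + 208.3) = 25,867, factor 1.06.

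At a factor of 1.32, a 1 SD comparison falls from 81% power to about 57%; at 1.06, to about 76%. Whether Cohort 1 has 17 per group is itself unconfirmed: 34 subjects in each of Cohorts 1, 2, 3 and 5 would need 136, against 100 targeted in Section VII.

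**The case against.** **The text shows only that a check is not written.** Section V.4 is a plain-language summary. Session B refers to earlier instructions to the subject, of which only the insulin part is stated, and the consent pages are not available here. Staff may well take a finger-stick, which would not count in the blood-volume row. This stands, and the point is limited to what is written. But Sessions C and D do write their checks, so leaving them out is not the plan's general style.

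**The stricter sessions carry more risk.** They infuse insulin and induce hypoglycemia. Session B gives no study insulin, and a nurse is present throughout. This too stands, and it keeps the point modest. It does not supply a glucose reading for subjects who may not notice a low.

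**A reader might infer that a planned Cohort 1 analysis is biased, with an inflated false-positive rate.** The documents do not support that:

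- The diagnosis-by-clamp interaction in Section V.6 is not tied to Cohort 1.
- Setting Session B against Session C's proton scan is an inference. The Session C figure note says only "After a set up period of approximately 30 minutes that includes a 1H MRS scan" and gives no glucose level for it.
- The blood-draw table has glucose near 55 mg/dL for only about 20-25 minutes at tracer start, so a 30-minute set-up could begin before stable hypoglycemia.
- Any false-positive rate would rest on an assumed slope, response shape and glucose distribution, and could be no more than the nominal level.

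Nor do the documents show that Session B glucose would be abnormal; Group 1 must have HbA1c below 7.5%.

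**Conclusion.** The point holds as a cheap improvement, first for safety and second for interpretability. Followed as written, T1DM subjects selected for hypoglycemia unawareness are scanned for an hour after usual insulin with no glucose reading and no low-glucose rule, and the state called euglycemic goes unrecorded. Any use of that scan as the euglycemic condition or as a group comparison then rests on an unknown glucose level.

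The size of any bias cannot be determined from the documents and may be nil. The conclusion assumes that the supplied text is the operative instruction. It does not reach the ketone endpoint or Cohorts 2, 3 and 5.

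**What to change.** For Session B in Cohort 1:

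1. Take and record a finger-stick glucose just before magnet entry and again after the acquisition, in both groups.
2. Do not scan below 70 mg/dL: treat and recheck, or reschedule. Reschedule above 200 mg/dL. State that these limits serve safety and plausibility, not bias control.
3. Tell T1DM subjects to eat their usual breakfast with their usual insulin, and give controls the same meal instruction. Do not ask for fasting unless insulin is reduced as in Session D, because fasting after a full dose would create the hazard.
4. Report Session B glucose by group. Treat any glucose-adjusted analysis as exploratory only, since it costs precision and assumes one slope for both groups, while the study asks whether T1DM responses differ.

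The cost is two finger-sticks per subject, a short paragraph in Session B, one schedule row, and a few delayed or rescheduled visits. No IV line is needed.

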To define the effect of alternate fuels on brain neurotransmitter metabolism in hypoglycemia unawareness we will compare its ability to modulate the oxidation of infused stable isotope-labeled glucose in healthy adults with that in age- and weight matched subjects with c-peptide-negative T1DM with a history of hypoglycemia unawareness. During clamped hypoglycemia all subjects will undergo an NMR spectroscopy scan that permits detection of the stable isotope used, which will be either carbon13 (¹³C) or deuterium (²H). Using isotopically labeled-glucose as a tracer together with a co-infusion of 350mM unlabeled lactate, we will measure neuronal glucose metabolite enrichment, visualize them in three dimensions and determine the time courses of enrichment. These will be fitted with our metabolic model to determine whether increased lactate stimulates PDH flux and glucose oxidation under hypoglycemia and to what degree this varies across different regions of the brain.

Subject Selection and Preparation:

Two groups of subjects aged 18-65 years will be studied:

- 1) Group 1 will be T1DM subjects (C-peptide negative, HbA1c <7.5%) with a history of severe hypoglycemia and hypoglycemia unawareness as assessed by the Ryan HYPO Score (see below) and as evidenced by interview, questionnaire and glucose log and/or continuous glucose monitoring.

- 2) Group 2 will be non-diabetic healthy subjects (fasting plasma glucose < 100 mg/dL, normal HbA1c) who are matched for age and gender to the type 1 diabetic subjects, to serve as controls for the study.

The Ryan HYPO score:

During a 4-week period subjects record blood sugar levels 5 times per day. On the occasion that the glucose recorded is <54 mg/dl subjects are asked to describe the details of the event using a questionnaire recently developed at Edmonton by Ryan et al. to more objectively define hypoglycemia severity. Particular emphasis in the questionnaire is devoted to the type of symptoms and whether help was required to

reverse the hypoglycemic event. From these data a composite HYPO score is generated based on the glucose readings and the patient's reported hypoglycemic events. A composite score in the upper quartile of T1DM control patients will be required for enrollment in this study.

Subjects will be placed into one of following cohorts:

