- E. Can donor-subjects withdraw their materials at any time, and/or withdraw the identifiers that connect them to their materials?
 - i. How will requests to withdraw materials be handled (e.g., material no longer identified: that is, anonymized) or material destroyed)?
- **F.** Describe the provisions for protection of participant privacy
- **G.** Describe the methods for the security of storage and sharing of materials

6. **Statistical Considerations:** Describe the statistical analyses that support the study design.

Sample size calculations were performed using PASS 2002 (Hintze J. 2001. NCSS and PASS Number Cruncher Statistical Systems. Kaysville, Utah.). In our preliminary magnetic resonance spectroscopy experiments (see preliminary studies), under hypoglycemic conditions, we observed significantly greater fractions of glial oxidative metabolism supplied by acetate in T1DM subjects compared to non-diabetic controls $(0.19 \pm 0.066 \text{ vs } 0.10 \pm 0.020; \text{ a } 90\% \text{ increase in diabetics compared to controls})$. We will expect differences between severe hypoglycemia unaware and control subjects in this study to be on a similar scale. With a pooled standard deviation of 0.033, our proposed sample sizes (17 diabetic subjects and 17 non-diabetic controls) will provide 80% power at the two-sided 0.05 significance level to detect differences of 0.033 between diabetic subjects and non-diabetic controls representing a 33% increase from non-diabetic subjects. In short, we should easily have sufficient numbers of to address our primary endpoint of enhanced ketone body uptake and metabolism following recurrent hypoglycemia. Using this data, our proposed sample sizes of 17 subjects per group will provide >80% power to detect a 20% difference in the severe hypoglycemia unaware compared to each control group. We anticipate the changes seen will be much greater than that. Because small effects cannot be detected with sufficient power, conclusions based on failure to reject the null hypothesis will be avoided.

The same group size considerations apply to the cohorts studied with glucose/lactate coinfusions and the cognitive performance analysis under ketone infusion outside of the MRI scanners.

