12. **Statistical Considerations:** Describe the statistical analyses that support the study design.

Sample size calculations were performed using PASS 2002 (Hintze J. 2001. NCSS and PASS Number Cruncher Statistical Systems. Kaysville, Utah.). In our preliminary magnetic resonance spectroscopy experiments (see preliminary studies), under hypoglycemic conditions, we observed significantly greater fractions of glial oxidative metabolism supplied by acetate in T1DM subjects compared to nondiabetic controls (0.19 \pm 0.066 vs 0.10 \pm 0.020; a 90% increase in diabetics compared to controls). We will expect differences between severe hypoglycemia unaware and control subjects in this study to be on a similar scale. With a pooled standard deviation of 0.033, our proposed sample sizes (17 diabetic subjects and 17 nondiabetic controls) will provide 80% power at the two-sided 0.05 significance level to detect differences of 0.033 between diabetic subjects and nondiabetic controls representing a 33% increase from nondiabetic subjects. In short, we should easily have sufficient numbers of to address our primary endpoint of enhanced ketone body uptake and metabolism following recurrent hypoglycemia. Using this data. our proposed sample sizes of 17 subjects per group will provide >80% power to detect a 20% difference in the severe hypoglycemia unaware compared to each control group. We anticipate the changes seen will be much greater than that. Because small effects cannot be detected with sufficient power, conclusions based on failure to reject the null hypothesis will be avoided.

Data analysis will be performed using SAS statistical software version 8.2. Prior to the fundamental analysis, all data will be appropriately screened for accuracy, missing data, outliers and agreement with assumptions for the analyses. Univariate descriptive statistics and plots will first be employed to determine out-of-range values as well as plausible means and standard deviations. Non-normal variables will be identified through the inspection of normal probability plots and with the Kolmogorov-Smirnov test. If required, appropriate transformations or non-parametric tests will be applied to variables in violation of the model assumptions. [name]., the GCRC biostatistician, is available for advice in data analysis.

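### With the plan's own inputs (SD 0.033, 17 per group, two-sided 0.05), power for a 20% difference from the control mean of 0.10 is about 40%, not above 80%

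*Combined protocol and SAP*

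**What the plan says.** Section V, item 6 (Statistical Considerations) gives pilot results for the fraction of glial oxidative metabolism supplied by acetate: 0.19 ± 0.066 in T1DM subjects and 0.10 ± 0.020 in non-diabetic controls, described as a 90% increase. Two power statements follow.

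- The first: "With a pooled standard deviation of 0.033, our proposed sample sizes (17 diabetic subjects and 17 non-diabetic controls) will provide 80% power". The test is two-sided with α = 0.05, and the difference in question is 0.033, described as "representing a 33% increase from non-diabetic subjects".
- The second, attributed to the same data: "17 subjects per group will provide >80% power to detect a 20% difference" between the severe hypoglycemia unaware subjects and each control group.

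The text then adds "We anticipate the changes seen will be much greater than that", and after that "Because small effects cannot be detected with sufficient power, conclusions based on failure to reject the null hypothesis will be avoided".

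Both power statements appear again in item 12 (Statistical Considerations) of the same section. Item 6 alone goes on to extend the group-size reasoning to the glucose/lactate and cognitive cohorts. For the analysis, both copies say "Group comparisons will be assessed by analysis of variance (ANOVA) for repeated measures".

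**The concern.** The first statement fixes the test, the SD (0.033) and the base for percentages (0.033 is 33% of 0.10). If 33% is the difference that 17 per group can detect with 80% power, a 20% difference on that base and SD must have clearly less than 80%. The second statement gives it more than 80%, with no new SD, base, significance level or design.

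At stake is the accuracy of the sample size justification. A reader would take the study to be sensitive to 20% effects. Item 6 invites the same reading for the glucose/lactate and cognitive cohorts, to which it applies the same group-size considerations. The next sentence, on expected changes, also uses 20% as its benchmark.

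**Working it through.** **Inputs, all from Section V, item 6.** n = 17 per group; two-sided α = 0.05; SD = 0.033; control mean 0.10; T1DM mean 0.19; pilot ± values 0.020 (controls) and 0.066 (T1DM).

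**Method.** Two-sample equal-variance t-test with df = 2 × 17 − 2 = 32 and critical value 2.037. Power comes from the noncentral t distribution with noncentrality δ = difference / (SD × √(2/n)). Here SD × √(2/17) = 0.033 × 0.343 = 0.01132.

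**Step 1: reproduce the plan's first figure.** Difference 0.033: δ = 0.033 / 0.01132 = 2.915, power **80.7%**. This matches the stated 80%, so the method is the right one. The smallest difference with 80% power is 0.0327, about 33% of 0.10.

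**Step 2: the 20% difference on the same base.** 20% × 0.10 = 0.020: δ = 0.020 / 0.01132 = 1.767, power **40.3%**. A normal approximation gives 42.4%.

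**Step 3: sample size for 80% power at 0.020.** 43 per group gives 79.3% and 44 per group gives 80.3%, so **44 per group**.

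**Step 4: can another reading rescue the claim?** All rows use a 20% difference.

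| Reading | Power |
|---|---|
| One-sided 0.05, otherwise as stated | 53.4% |
| Log scale, CV 0.33 | 36.1% |
| 17 vs 34 controls | 51.6% |
| Mean of 2 measurements per subject, correlation 0.5 (assumption) | 50.8% |
| Mean of 2 uncorrelated measurements per subject (assumption) | 67.8% |
| Mean of 3 uncorrelated measurements per subject (assumption) | 84.3% |
| SD 0.020 (the control ± value) in place of 0.033 | 80.7% |
| 20% of the T1DM mean: 0.2 × 0.19 = 0.038, SD 0.033 | 90.2% |

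The last three rows exceed 80%, and each changes an input. Three uncorrelated measurements amount to an effective SD of 0.033/√3 = 0.019. At n = 17, a difference of 0.020 reaches 80% power only if the effective SD is about 0.0202 or smaller.

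**Side check on the SD.** If the two ± values are SDs and are weighted equally, the pooled SD is √((0.066² + 0.020²)/2) = 0.0488, not 0.033. With 0.0488, power is 21% for 0.020 and 48% for 0.033. A value of 0.033 would put a weight of about 17% on the diabetic variance: (0.033² − 0.020²)/(0.066² − 0.020²) = 0.174. The documents give neither the pilot group sizes nor whether ± means SD or SEM, so this is a question and not a finding.

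**The case against.** Five points can be made for the plan.

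1. *The figure has a plausible origin in the same paragraph.* The control ± value is 0.020. A difference of 0.020 with SD 0.020 has a standardized effect of 1.0, exactly as 0.033 with SD 0.033 does, and the same 80.7% power. The fault may therefore be an undeclared switch of SD. That stands as an explanation, but the SD the paragraph states for its power calculation is the pooled 0.033.
2. *Repeated measurements could raise power.* The planned ANOVA does not say how many measurements per subject enter. Three or more would be enough if they were uncorrelated. Zero correlation within a subject is unrealistic, though, and the plan does not invoke averaging in its power statement.
3. *The base is not certain.* The 20% sentence refers to each control group. The Research Plan says "Two groups of subjects aged 18-65 years will be studied" and defines only one as controls, yet under the Ryan HYPO score it also says "A composite score in the upper quartile of T1DM control patients will be required for enrollment in this study". Against a T1DM reference near 0.19, power would be 90%. Both percentages the paragraph does work out (90% and 33%) use 0.10, and the claim fails against the only control group defined. What the phrase refers to remains a fair query.
4. *40% itself depends on an SD whose source is unclear.* This is true, and it argues for settling the SD before a new figure is printed. It does not help the claim, since the equal-weight SD would lower power further.
5. *The consequence is small.* This also stands. For the expected difference of 0.19 − 0.10 = 0.09, power exceeds 99.9% at SD 0.033 and is 99.9% at 0.0488. The correct 33% figure is already printed, and the plan says it will not draw conclusions from null results.

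**Conclusion.** The concern holds. As written, the power for a 20% difference is about half the claimed minimum (40.3% against more than 80%), and it contradicts the correct 33% statement in the same paragraph. Nothing elsewhere in the document reconciles the two.

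The 40% figure assumes a two-sample t-test, SD 0.033 as given, and 20% taken of the control mean 0.10. The first two assumptions reproduce the plan's own 80%, and the third is the base it uses for 33%.

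This does not show that the study is underpowered for the effect it expects, and it does not alter the sample size. It is an error in a stated operating characteristic that should be corrected.

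**What to change.** Make the same change in items 6 and 12 of Section V.

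- If another SD or base was intended for the 20% figure, state it and say why it applies to this comparison.
- Otherwise delete the 20% sentence, or replace it with: *At SD 0.033, 17 per group gives 80% power for a 33% difference (0.033); power for a 20% difference (0.020) is about 40%.*
- In either of those last two cases, reword the next sentence, which uses 20% as its point of comparison.

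Two queries should be answered at the same time: (a) which comparison is meant by each control group; (b) how the pooled SD of 0.033 follows from 0.066 and 0.020, giving the pilot group sizes and whether ± is SD or SEM. Query (b) should be settled before any revised power figure is inserted, because that figure depends on it.

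The cost is wording in two places, with no extra subjects and no change to the analysis. The one drawback is that the stated detectable effect becomes less favourable.
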